## **II. Background & Significance**

Urinary incontinence (UI) is a very common condition affecting women of all ages. UI is an emotionally, socially, physically and economically burdensome condition (1). It has a significant impact on quality of life (QOL), where urinary incontinence has been shown to be associated with embarrassment, anxiety, and depression. Total costs of UI (direct and indirect) are about \$11 billion/a year (2).

The influence of the human microbiota on normal health and disease conditions is increasingly appreciated in a variety of medical fields (3). The hypothesis of “sterile” bladder has recently been disputed (4), leading to a series of investigations about the role of urinary microbiota in urinary incontinence. Stress urinary incontinence does not appear to be associated with urinary microbiota (5), while urgency urinary incontinence (UUI) is highly related to microbial status and diversity (4,5). The role of inflammation in relation to urinary microbiome is understudied among women treated for UUI. An important emerging question is whether the inflammatory milieu and urinary microbiota interact and vary over time, and in particular, in response to UI treatment.

Data from the Anticholinergic Versus Botulinum A Comparison (ABC) Trial showed that women with sequence-positive urine samples (DNA positive) responded better to treatment (anticholinergics or botulinum toxin A) and had decreased number of UUI episodes (6). Furthermore, those women had less urinary tract infections (6). A study solely devoted to analyzing the role of urinary microbiome in the treatment of UUI with solifenacain (anticholinergic) showed changes in microbial abundance after 12-week treatment (7). Clinically, many women with UUI fail pharmacologic treatment options with anticholinergics.

We hypothesize that an increased inflammatory response due to an altered urinary microbiome at baseline predisposes women to a higher rate of failure of UUI treatment with anticholinergic medications. The objective of this pilot study is to better understand the urinary microbiome and associated inflammatory markers in blood and urine in women with UUI, and whether they vary over time secondary to anticholinergic treatment. To address this goal, we plan to enroll 20 women with UUI presenting to our Urogynecology Clinic.

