## VI: Statistical Considerations

Descriptive statistics will be employed to describe and compare data using parametric statistical tests for normally distributed data and non-parametric tests for non-normally distributed data. We will then specifically evaluate the role of microbiome on UUI in our subgroups. Wilcoxon test and Mann Whitney test will be applied to estimate the possible differences. The correlation between microbiome and inflammatory markers before and after treatment will be assessed by the Spearman's rank correlation. Harvard Catalyst Statisticians will be consulted for statistical analysis.

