Inflammation in Women with Urgency Urinary Incontinence Treated with Anticholinergics

Version Date: 7/28/2022

ID: 2018P000980

Study Name: Inflammation in Women with Urgency Urinary Incontinence Treated with Anticholinergics

PI Name: [name]

Prepared by: [name], B.S., Research Assistant

Specific Aim 1: To assess inflammatory markers in urine and serum before and after a 6-week treatment course with anticholinergics.

Specific Aim 2: To determine the role of the urinary microbiome in relation to inflammation before and after a 6-week treatment course with anticholinergics.

Study Population: This study is a prospective pilot of women who have a diagnosis of urge urinary incontinence (UUI) and present to the BWH Urogynecology Clinics in Boston or Foxborough. This study enrolled 20 women offered standard of care anticholinergic treatment for 6 weeks.

Statistical Methods: Demographic and clinical characteristics were summarized with the absolute count and percent of categorical variables and median and interquartile range of continuous variables. No comparison was made as demographic and clinical characteristics did not change in follow-up period.

Plasma and combined (baseline and follow-up) urine cytokines were summarized using median and interquartile range.

Urine cytokines at baseline and follow-up were tested for normality using Shapiro-Wilks test for normality. The data were found to be non-normal and thus were summarized using median and interquartile range. Urine cytokines were compared from baseline to follow-up for most patients (only 13 of the 20 patients returned for follow-up) using t-test of Wilcoxon rank sum. P value of <0.05 was considered significant.

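### The SAP specifies no estimate or confidence interval for the within-woman change in urine cytokines, so with 13 pairs a non-significant result cannot exclude a large change

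*SAP*

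**What the plan says.** Aim 1 in both documents is "To assess inflammatory markers in urine and serum before and after a 6-week treatment course with anticholinergics". The protocol's objective (section II) asks of the microbiome and the markers "whether they vary over time secondary to anticholinergic treatment".

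Under Statistical Methods, the SAP gives three outputs for urine cytokines:

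- a summary of baseline and follow-up values combined;
- a summary at each visit: "The data were found to be non-normal and thus were summarized using median and interquartile range";
- a comparison between visits "using t-test of Wilcoxon rank sum", with the note that "only 13 of the 20 patients returned for follow-up", and the decision rule "P value of <0.05 was considered significant".

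The protocol (section VI) says "Wilcoxon test and Mann Whitney test will be applied to estimate the possible differences". It speaks of estimating but names only tests. Neither document mentions a within-woman difference or ratio, a median change, a Hodges-Lehmann estimate or a confidence interval.

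**The concern.** The one inferential result per cytokine is a P value set against 0.05. The medians and interquartile ranges beside it describe how women differ from each other at a visit. The size of the change within a woman, and how precisely it is known, cannot be recovered from them.

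This comparison carries the before/after part of Aim 1. Blood is drawn only at enrolment (protocol section III), so urine is the only fluid measured at both visits. Followed exactly, the plan can say whether each cytokine passed a threshold. It cannot say how large a change was seen, or which changes the data rule out. In a pilot with at most 13 pairs the second question matters most, because many sizeable changes will miss the threshold. A follow-on study would also inherit no effect size and no SD of change.

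**Working it through.** The documents contain no power, effect size, SD or precision figure, so there is nothing of the plan's own to reproduce.

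**Inputs**

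- Pairs: n = 13, the most possible (SAP, Statistical Methods).
- Significance level: 0.05 (SAP). Sidedness is not stated; two-sided is assumed.
- Pairing: assumed. The SAP's wording names the rank-sum test, which is for independent samples.
- SD of the within-woman change: not in the documents. It serves as the unit, on a scale where changes are roughly normal. For fold changes, an SD of the natural-log change of 0.5 to 1.5 is assumed.

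**1. Half-width of the 95% interval.** t(0.975, 12)/√13 = 2.179/3.606 = 0.604 SD. A result that just misses significance has an interval from 0 to about 2 × 0.604 = 1.21 SD.

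**2. Power of the paired t-test.** Noncentral t, 12 degrees of freedom, noncentrality δ√13:

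| True change δ (SD) | Power |
|---|---|
| 0.2 | 10% |
| 0.5 | 38% |
| 0.8 | 75% |
| 0.847 | 80% |
| 0.98 | 90% |

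The normal approximation for 80% power, (1.960 + 0.842)/√13 = 0.777 SD, is slightly optimistic at this sample size.

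**3. Signed-rank test and its interval.** There are 13 × 14/2 = 91 Walsh averages. The exact two-sided test rejects when the smaller rank sum is 17 or less, with one-sided probability 0.0239. The matching Hodges-Lehmann interval runs from the 18th smallest to the 18th largest Walsh average, with confidence 1 − 2 × 0.0239 = 95.2% when there are no ties. In simulated normal data its median half-width is about 0.60 SD, as in step 1. Power at 0.5 SD is 36% (100,000 simulations), so such a change is non-significant 64% of the time.

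**4. What a non-significant result leaves open.** In 4,000 simulated samples with no true change, about half of the non-significant results had an interval reaching 0.8 SD or more, and 95% had one reaching 0.5 SD or more. With a true change of 0.5 SD, 76% reached 0.8 SD.

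**5. As fold changes.** With s the assumed SD of the log change, the interval is the estimate multiplied and divided by exp(0.604s). A just non-significant result extends to exp(1.209s):

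| s | Interval factor | Fold change still allowed |
|---|---|---|
| 0.5 | 1.35 | 1.8 |
| 0.75 | 1.57 | 2.5 |
| 1.0 | 1.83 | 3.3 |
| 1.5 | 2.48 | 6.1 |

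**6. Comparison.** Had all 20 women returned, the half-width would be 0.47 SD and the change detectable with 80% power 0.66 SD.

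**The case against.** The strongest reply is that this is a 20-woman pilot with no power claim, and that no stated result is shown to be wrong. That is fair: the omission limits what can be learned and does not invalidate the data. But a pilot has more use for estimates with intervals than for a threshold, and nothing in the SAP commits the authors to add them.

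A second reply is that the figures presuppose a paired analysis, while the SAP names an unpaired test and calls the data non-normal. This stands as a condition on the numbers. The test needs correcting too, but a corrected test alone would still deliver only a P value.

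Third, the remedy has limits:

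- A ratio needs positive, quantifiable values at both visits, and the documents do not say how undetectable values are handled.
- The signed-rank interval assumes roughly symmetric log changes.
- Under normality, an SD from 13 women has a 95% interval from √(12/23.34) = 0.72 to √(12/4.40) = 1.65 times the estimate, so its planning value is modest.

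A reader might also infer more than the documents support:

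- That the two visit medians point in a misleading direction. A difference of medians is not the median difference, but how often their signs part depends on spreads, correlations and effects that neither document gives. In small samples the within-woman median is itself often wrong in sign.
- That the authors treat non-significance as proof of no change. The SAP says only what counts as significant.
- That Aim 1 itself asks about variation over time. That wording belongs to the objective in protocol section II; Aim 1 speaks of assessment before and after treatment.

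**Conclusion.** The point holds as an omission that should be repaired: the before/after comparison of urine cytokines is planned without an effect size or a measure of precision. The sizes found in the working (half-width about 0.60 SD, 80% power at about 0.85 SD, a 0.5 SD change missed about 64% of the time) rest on 13 complete pairs, a paired two-sided analysis at 0.05, and changes that are roughly normal on the chosen scale. The fold-change figures rest further on assumed SDs of the log change. The gap itself depends on none of these assumptions, since it is visible in the text. Under them, P ≥ 0.05 cannot exclude a large change. It does not follow that any reported conclusion is wrong.

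**What to change.** For each urine cytokine, in the SAP and the results table:

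- State the number of pairs.
- Beside a paired signed-rank P value, report the Hodges-Lehmann estimate of the within-woman follow-up/baseline ratio with its matching 95% interval (exact level about 95.2% at 13 pairs without ties). Where values are zero or undetectable, use the difference instead.
- Give the SD of the change on the same scale.
- Interpret non-significant results by the interval, as the range of changes the data do not exclude.
- Note that the estimate applies to the 13 of 20 women who returned.

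The cost is a few extra table entries and a few sentences, from data already in hand. The price to accept is that the intervals will be wide and that they rest on roughly symmetric log changes, which should be stated.
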